1.0 Background and Rationale

1.1 Background/Standard Therapies

Breast cancer is the most frequently diagnosed cancer and the second leading cause of cancer death in women in the United States. Despite a decrease in the overall incidence of breast cancer, more than 40,000 women are expected to die of this disease each year[1]. Despite improvements in therapy, patients with locally advanced or metastatic disease eventually relapse and die from their disease. Investigating treatments aimed at improving outcome is critical, and finding new targeted treatment that could delay disease progression would significantly advance the care of women with this common malignancy.

The majority of breast cancers express receptors for either or both estrogen and progesterone; this finding indicates responsiveness to hormone therapy [2]. For postmenopausal women with hormone-receptor positive advanced stage disease, suppression of estrogen with third generation aromatase inhibitors (AI) is more effective than tamoxifen for first-line endocrine treatment, and AIs have been demonstrated to improve disease free survival compared to tamoxifen in women with early stage, hormone receptor positive disease[3]. However, the major limitation of endocrine therapy remains the near universal development of resistance in the advanced setting, and recurrence despite hormone therapy due to resistance in the early stage setting. Although there are no proven clinical strategies to reverse or prevent endocrine therapy resistance, several pre-clinical investigations suggest opportunities for therapeutic intervention[4]. This trial is designed to evaluate whether anti-VEGF therapy with pazopanib can reverse resistance and prolong progression-free survival when added at the time of progression to endocrine therapy with AIs for hormone-receptor positive metastatic breast cancer.

Angiogenesis and estrogen

Angiogenesis, the formation of new blood vessels, is essential for the development, progression, and metastasis of malignant tumors[5-7]. Vascular endothelial growth factor (VEGF) is a primary stimulus of angiogenesis in tumors and functions through binding VEGF receptor-2 (VEGFR2; also known as flk/kdr) and VEGF receptor-1 (VEGFR1; also known as flt) expressed on endothelial cells[7].

Endothelial cells exposed to the supernatants of estradiol treated breast cancer cells develop increased levels of VEGFR2 compared to controls. This increase in VEGFR2 supports previous findings that endothelial cells containing estrogen receptors exhibit a proliferative response to estradiol[8-10]. In addition, estrogen has been associated with the inhibition of apoptosis of cultured human endothelial cells, and therefore indicates the creation of a pro-angiogenic environment[10].

Estradiol increases intracellular levels of VEGF mRNA and protein in breast cancer cell lines as well as extracellular levels of VEGF protein [11]. Additionally, estradiol treatment of breast cancer cell lines decreased extracellular sVEGFR1, a soluble form of VEGFR1 that is believed to sequester extracellular VEGF and act as an antiangiogenic factor[11, 12]. This decrease was also observed in an *in vivo* xenograft models of breast cancer in nude mice[12].

These data indicate that estrogen acts directly on breast cancer cells to induce angiogenesis by creating a proangiogenic environment. Furthermore, subjects whose tumors have lower sVEGFR1/VEGF ratios tend to have a poorer prognosis compared to those with higher ratios[13, 14]. VEGF may be an important target for hormone receptor-positive breast cancer[15]. In patients with operable breast cancer, neoadjuvant antiestrogen therapy with tamoxifen reduced breast cancer angiogenesis in responding tumors as measured by microvessel count (MVC)[16].

These data support the hypothesis that estradiol can modulate angiogenesis in breast cancer, and that angiogenesis is one mechanism of resistance to hormone directed therapy. Both estrogen and angiogenesis are essential for the development and progression of breast cancer, making the targeting both pathways in combination appealing.

1.2 Investigational Therapy

Pazopanib

Pazopanib is a potent, multi-targeted TKI of VEGFR-1, -2, -3, PDGFR- α and - β and c-kit, with IC₅₀ values of 10, 30, 47, 71, 84 and 74 nM, respectively[17]. It inhibits VEGF-induced VEGFR-2 phosphorylation in human umbilical vein endothelial cells (HUVEC) as well as in mouse lungs in a dose-dependent manner. Pazopanib shows significant growth inhibition of a variety of human tumor xenografts in mice, and also inhibits bFGF- and VEGF-induced angiogenesis in two mouse models of angiogenesis, the Matrigel™ plug assay and the cornea micropocket model.

To date, the safety experience includes over 1200 cancer subjects who have been treated in pazopanib studies. Over 850 subjects have received pazopanib monotherapy; the monotherapy safety profile described is based on 225 subjects with renal cell cancer treated with pazopanib. The most common AEs occurring in $\geq 10\%$ of subjects in decreasing order of frequency were diarrhea, fatigue, hair depigmentation, nausea, hypertension, dysgeusia, headache, anorexia, rash, vomiting, abdominal pain, cough, arthralgia, and constipation. Elevations in ALT of any Grade were reported in 50% of subjects with Grade 3 elevations in 6% and Grade 4 in < 1%. AST and ALT elevations occurred in parallel. Hyperbilirubinemia of any Grade occurred in 29% of subjects with Grade 3 elevations in 2%. No Grade 4 elevations have been reported. Concomitant elevations in transaminases and bilirubin have been observed in less than 1% subjects. Uncommon ($\leq 1\%$) but significant adverse events have been reported including: pulmonary embolism, venous thrombosis, hemorrhage, bowel perforation, myocardial infarction/angina, cerebrovascular accidents/TIA, atrial fibrillation, renal failure, and seizures.

Anemia, leukopenia, and thrombocytopenia were reported in 14 – 20% of subjects with Grade 3/4 abnormalities being uncommon ($\leq 2\%$). Hyponatremia of any grade was observed in 32% of subjects; with Grade 3 or 4 hyponatremia in 7% of subjects. Hyperkalemia of any grade was reported in 21% of subjects with Grade 3 or 4 hyperkalemia in 3% of subjects. Hyponatremia and hyperkalemia have not occurred concurrently in the same subject to suggest adrenal insufficiency. Increase in creatinine of any grade was reported in 25% with Grade 3 or 4 events in 1%. Elevations in amylase and lipase of any

grade were reported in 16% and 17% respectively, with Grade 3 events in 1% and 5% respectively. Pancreatitis was reported in one subject. Increase in TSH was reported in 24% and a decrease in T4 in 18% of subjects.

Serial ACTH stimulation tests were conducted in two Phase I and two Phase II trials in cancer subjects. Adrenal insufficiency was not observed in 47 subjects for whom data was available. Twenty one of the 47 subjects had data beyond 24 weeks and 5 had data beyond 52 weeks. Additional pazopanib information is included in the pazopanib investigator brochure (IB).

In October, 2009, the U. S. Food and Drug Administration granted approval to pazopanib tablets (VOTRIENTTM, Novartis Pharmaceuticals) for the treatment of patients with advanced renal cell carcinoma.

The efficacy and safety of pazopanib were evaluated in an international, multicenter, randomized, double-blind trial comparing pazopanib to placebo in renal cell carcinoma who were treatment naïve or who had received prior cytokine therapy. All patients received best supportive care. The trial was conducted in patients with metastatic renal cell carcinoma stratified according to performance status, prior nephrectomy, and prior cytokine therapy.

A total of 435 patients were randomized (2:1) to receive pazopanib (n=290) or placebo (n=145). Demographics were balanced between the two arms. Progression-free survival (PFS) was the trial's primary endpoint. The median PFS was 9.2 and 4.2 months in the pazopanib and placebo arms, respectively (HR = 0.46, p value < 0.001). The effect was observed in both subgroups: treatment naïve (HR = 0.40) and cytokine pre-treated (HR = 0.54). After documented radiological progression, patients receiving placebo could receive pazopanib.

The overall survival results are not mature; 40% of patients had died by the time of data cut-off. The objective response rates were 30% and 3% for pazopanib and placebo, respectively. The median duration of responses was 13.5 months.

The most common adverse reactions (greater than or equal to 20%) were diarrhea, hypertension, hair color changes, nausea, anorexia, and vomiting. Grade 3/4 adverse reactions that differed by greater than or equal to 2% between arms were abnormal hepatic function, diarrhea, hypertension, and proteinuria. QT prolongation has been seen with pazopanib. Laboratory abnormalities occurring in >10% of patients and more commonly (>5%) in the pazopanib arm included increased transaminases, hyperglycemia, leukopenia, hyperbilirubinemia, neutropenia, hypophosphatemia, thrombocytopenia, lymphocytopenia, hyponatremia, hypomagnesemia, and hypoglycemia. Deaths due to serious adverse events include cerebrovascular accident, gastric cancer, gastrointestinal hemorrhage, hemoptysis, bowel perforation, cardiac failure, myocardial infarction, hepatic failure and pneumonia occurred more commonly in the pazopanib arm. Hepatic dysfunction is included as a boxed warning in the product label and two deaths were associated with hepatic failure.

Recently, a phase II trial was designed for patients with metastatic breast cancer, who failed 2-3 prior chemotherapy. Total 20 patients were recruited in this study, 70% were ER+, and all were Her-2/neu negative. Pazopanib monotherapy was given at 800 mg daily. One patient (5%) had a partial response, 11 (55%) had stable disease (SD) [four (20%) with SD > or = 6 months], and seven (35%) had progressive disease as their best response. One (5%) was not evaluable. The median time to progression was 5.3 months. Pazopanib did not cause significant severe toxicity aside from grade 3-4 transaminitis, hypertension, and neutropenia in three patients each (14% each) and grade 3 gastrointestinal hemorrhage in one patient (5%)[18].

Standard therapy for hormone receptor positive metastatic disease.

Randomized phase III trials have demonstrated superiority in terms of response and in some settings TTP, for anastrozole, letrozole and exemestane compared to tamoxifen in the first-line metastatic setting[19]. The Tamoxifen or Arimidex Randomized Group Efficacy and Tolerability (TARGET) trial, 668 post-menopausal women (approximately 45% of whom were either ER or PgR positive while 55% had a tumor with unknown ER/PR status) were randomized (1:1) to receive either anastrozole or tamoxifen for the treatment of MBC. Time to progression (TTP) of the subgroup of subjects with hormone receptor positive tumors was 8.9 months for subjects administered anastrozole compared to 7.8 months for subjects treated with tamoxifen (statistical analyses for the sub-populations were not performed). Treatment was well-tolerated in both arms, although the notable adverse events for tamoxifen (thromboembolic events and vaginal bleeding) were significantly lower for subjects in the anastrozole arm[20].

A second Phase III trial randomized 916 patients with treatment naïve metastatic breast cancer (hormone receptor-positive or unknown tumors) to receive letrozole 2.5 mg or tamoxifen 20 mg daily. Treatment with letrozole resulted in a significantly longer median TTP than treatment with tamoxifen (9.4 months vs. 6.0 months, $P < .0001$)[21]. The incidence and severity of AEs were similar for letrozole and tamoxifen arms. Adverse events considered to be related to the study drug were also similar frequency (38% for letrozole and 37% for tamoxifen) and were similar in nature for both arms.

Lastly, exemestane was compared to tamoxifen in 371 patients with MBC (182 exemestane, 189 tamoxifen). Overall response rate was greater for exemestane than for tamoxifen treatment (46% v 31%; odds ratio = 1.85; 95% CI, 1.21 to 2.82; $P = .005$) as was median progression-free survival (PFS) (9.9 months; 95% CI, 8.7 to 11.8 months vs. 5.8 months; 95% CI, 5.3 to 8.1 months) [22]. Subsequent trials have demonstrated that hormone therapy is effective in sequence, that the order of therapy is not clearly important, and that the nonsteroidal (letrozole and anastrozole) and steroid AI (exemestane) are non-cross resistant. Given the above data, AIs have become a standard hormone therapy for the treatment of post-menopausal women with hormone receptor positive MBC.

1.3 Rationale for the Combination of Aromatase Inhibitor and an Angiogenesis Inhibitor

Angiogenesis, the formation of new blood vessels, is essential for the development, progression, and metastatic growth of malignant tumors [23, 24]. Vascular endothelial

growth factor (VEGF) is a primary stimulus of angiogenesis in tumors and functions through binding VEGF receptor-2 (VEGFR2; also known as flk/kdr) and VEGF receptor-1 (VEGFR1; also known as flt) expressed on endothelial cells [25].

Preclinical research has demonstrated that endothelial cells exposed to the supernatants of estradiol treated breast cancer cells develop increased levels of VEGFR2 compared to controls [26]. This increase in VEGFR2 supports previous findings that endothelial cells containing estrogen receptors exhibit a proliferative response to estradiol [27, 28]. In addition, estrogen has been associated with the inhibition of apoptosis of cultured human endothelial cells, and therefore indicates creation of a proangiogenic environment [28]. *In vitro* studies have revealed that estradiol increases intracellular levels of VEGF mRNA and protein in breast cancer cell lines as well as extracellular levels of VEGF protein [11]. Additionally, estradiol treatment of breast cancer cell lines decreased extracellular sVEGFR1, a soluble form of VEGFR1 that is believed to sequester extracellular VEGF and act as an antiangiogenic factor [11, 12].

The effect of estrogen on angiogenesis was further demonstrated using *in vivo* xenograft breast cancer models [12, 29]. In one study, ovariectomized nude mice bearing slow-release estrogen or placebo pellets were injected subcutaneously with a mixture of MCF-7 cells and Matrigel. The Matrigel–MCF-7 cell plugs were excised after 6 days and VEGFR was analyzed. Levels of VEGFR-1 protein were lower in Matrigel-embedded MCF-7 cells from mice implanted with estrogen pellets than in Matrigel-embedded MCF-7 cells from mice with placebo pellets. This decrease in VEGFR-1 expression was associated with a pronounced increase in the angiogenic response, reflected by a statistically significant increase in vascular density measured in the Matrigel plugs from estrogen-treated mice compared with vascular density measured in the Matrigel plugs from placebo-treated mice [12]. In another xenograft breast cancer model, castration in a male mouse model bearing androgen-dependent breast cancer led to tumor shrinkage and vascular regression. However, endocrine resistance emerged in this tumor model and was heralded by a wave of neovascularization and tumor regrowth. On a molecular level, castration initially causes a reduction in *VEGF* mRNA levels that parallels tumor and vascular regression. At the time of tumor regrowth, *VEGF* mRNA levels simultaneously rebound. Interestingly, castration in this model led to endothelial cell apoptosis before tumor cell apoptosis, supporting a direct effect of endocrine therapy on tumor vasculature. These data indicate that estrogen acts directly on breast cancer cells to induce angiogenesis by creating a proangiogenic environment [29].

In the clinical setting, patients with metastatic breast cancer, who had high VEGF levels in tumor tissue by ELISA, had lower response to first-line endocrine therapy compared with patients who had low VEGF levels in a multivariate analysis ($p=0.025$). In addition, a trend towards shorter PFS ($p=0.075$) was also seen [30]. In a randomized trial of tamoxifen in premenopausal women in the adjuvant setting, the benefits of tamoxifen for 2 years were significantly decreased in patients with high tumor-specific VEGFR2 expression by immunohistochemistry[31].

The addition of antiangiogenic therapy to hormonal therapy has been investigated in several clinical trials. In a phase II single arm study, 27 patients with metastatic breast cancer who progressed on endocrine therapy alone were recruited. Patients were continued on the same hormone therapy to which they had become refractory with the addition of bevacizumab. Stable disease was seen in 18 patients (66%) [32]. In a multi-center feasibility trial performed at MSKCC and UCSF, 43 patients with treatment naïve metastatic ER positive breast cancer, stable or responding to NSAI treatment were treated with the combination of letrozole and bevacizumab. 74% of the patients had clinical benefit with a favorable PFS of 17.1 months compared with a 9-month historical PFS in postmenopausal women with MBC treated with letrozole alone in the first-line setting [33]. This study led to an ongoing Phase III trial with the U.S. cooperative group CALGB testing this combined therapy.

These data suggest that co-targeting the tumor with endocrine therapy as well as its associated vasculature using anti-angiogenic agents could lead to additive effects, resulting in more effective anticancer therapy, and potentially reversing acquired resistance to hormone therapy [34].

In this trial, we propose to evaluate the role of VEGFR blockade with the tyrosine kinase inhibitor pazopanib in combination with nonsteroidal aromatase inhibitors (NSAI) in patients who are progressing or have relapsed on the same NSAI hormone therapy given for advanced or early stage breast cancer. If this trial demonstrates clinical benefit, this all oral combination could be tested in both the neoadjuvant and metastatic settings in a randomized phase II design.

In order to investigate potential factors predicting response or resistance to pazopanib and NSAIs, several translational studies have been incorporated into this trial.

The prognostic value of circulating tumor cells (CTC) has been demonstrated in several studies in breast cancer, especially in advanced stage [35-38]. At UCSF in the laboratory of [name], we have demonstrated expertise in the measurement of CTC in patients with advanced stage breast cancer by IC/FC assay. CTC are first enriched with immunomagnetic beads coated with EpCAM, then EpCAM+, CD45-, nucleic acid+ cells are detected by flow cytometry. This technique is highly sensitive and reproducible, and allows sorting of cells for molecular analysis as well as analysis of cell surface markers[39]. In this trial, we will collect patient's peripheral blood samples every 4 weeks while on treatment and follow any reduction of CTC.

The mechanisms of hormonal resistance includes intrinsic and acquired pathways: decreased ER expression accounts for intrinsic resistance and the increased receptor tyrosine kinase pathway relates to acquired resistance [40-42]. We plan to analyze the mutation of PI3K/Akt and deletion of PTEN by sequencing in CTC (depending on numbers of cells, which in turn determines feasibility), in order to make a preliminary assessment of potential markers of response to pazopanib.

The tumor microenvironment plays an important role in cancer development and progression. Clinical studies have revealed that the increased T regulatory cells (Treg), high ratios of

CD4/CD8 T lymphocytes, and extrafollicular B cells in primary tumors correlated with worse overall survival [43-45]. Recently, studies from preclinical models have shown that tumor associated macrophages (TAM) can promote pulmonary metastases in breast cancer animal models, and in both the preclinical and clinical settings are associated with worse clinical outcome [46-48]. TGF β has been linked to hormonal resistance in breast cancer. The activation of TGF β leads to increased regulatory CD4 $^{+}$ T cells and decreased cytotoxic CD8 $^{+}$ T cells in the tumor microenvironment [49]. A recent study in non-small cell lung cancer suggests that baseline and posttreatment levels of cytokines, particularly IL-4 and IL-12 correlated with response to pazopanib[50]. In this study, we will collect patients's serum to monitor the level of cytokines at baseline and during treatment, we will compare the change of cytokine level with pazopanib in each patient, and also compare between responders and non-responders. This information may help us to identify biomarkers that would predict response to antiangiogenic therapy and to identify possible mechanisms of resistance.

2.0 Objectives

2.1 Primary Objectives:

- To evaluate the clinical benefit rate (including complete response, partial response, and stable disease) at 12 weeks from the addition of pazopanib to a non-steroidal aromatase inhibitor (NSAI) (letrozole or anastrozole) in patients with hormone receptor positive advanced breast cancer progressing on the same NSAI hormone therapy.

2.2 Secondary Objectives:

- To evaluate progression free survival in patients treated with the combination of pazopanib and a NSAI.
- To evaluate safety of the combination of pazopanib and a NSAI.

2.3 Exploratory objectives:

- To quantify CTC as a surrogate marker of response.
- To evaluate specific markers including estrogen receptor, PI3K/AKT and PTEN on CTC at the time of study entry
- To evaluate the immune signature in serum samples from patients enrolled in this trial, including: IL-6, IL-8, VEGF, sVEGFR2, E-selectin, GRO-1, IL-4, IL-16, IP-10, IL-12, CSF-1, TIMP-1, OPN, HGF, SDF-1a and TRAIL.

3.0 Study Design and Eligibility Criteria

3.1 Study Design

This is a nonrandomized, open label, multicenter phase II trial to evaluate the efficacy of pazopanib in combination with a NSAI in patients with advanced breast cancer.

Patients with metastatic breast cancer progressing or relapsing on a NSAI will be eligible for enrollment in this study. Progression must be documented by radiographic studies. This will be a two-step protocol; 14 patients will be enrolled initially. If at least 1 response (response defined as clinical benefit) is observed in the first 14 patients at 12 weeks, we will proceed to

the second stage, where an additional 13 patients will be enrolled. We plan to enroll a total of 30 patients at 2 sites: UCSF and Yale Cancer Center (Yale), expecting that up to 3 patients will be un-evaluable due to unexpected events.

Treatment will consist of pazopanib, 800 mg a day by mouth and continuation of the NSA1 (letrozole, 2.5 mg a day, or anastrozole, 1 mg a day) the patient was taking at the time of progression. This treatment will be continued until progression or toxicity. Dose reduction of pazopanib for toxicity will be allowed. Patients will be evaluated by serial radiographic studies as well as circulating tumor cells. The primary endpoint is clinical benefit rate at 12 weeks.

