3.2 Inclusion Criteria

A subject will be considered eligible for inclusion in this study only if all of the following criteria are met:

1. Subjects must provide written informed consent prior to performance of study specific procedures or assessments, and must be willing to comply with treatment and follow up.
 - a. Procedures conducted as a part of routine clinical management of the subject (e.g., blood count, imaging study) and obtained prior to signed informed consent may be utilized for Screening or Baseline purposes provided these tests are obtained as specified in the protocol).
2. Subjects must have measurable or evaluable disease. Disease sites that are evaluable for progression but not measurable per RECIST guidelines version 1.1 include:
 - a. Bone lesions
 - b. Previously irradiated lesions
 - c. Cutaneous manifestations (non-discrete lesions only)
3. Age \geq 18 years.
4. Postmenopausal women defined by one of the criteria:
 - a. No spontaneous menses for at least 12 months if the subject is \geq 50 years old;
 - b. Amenorrheic for at least 12 months if the subject is < 50 years old, with serum estradiol within the institutional postmenopausal range;
 - c. Bilateral oophorectomy;
 - d. If prior hysterectomy but intact ovaries, must be \geq 55 years old, or have serum estradiol within the postmenopausal range;
 - e. If premenopausal, must be on a GnRH agonist (leuprolide or goserelin) with serum estradiol levels within the institutional postmenopausal range.
5. Eastern Cooperative Oncology Group (ECOG) performance status (PS) \leq 2.
6. Histologically or cytologically confirmed estrogen receptor (ER) and/or progesterone receptor (PgR) positive carcinoma of the breast with unresectable, locally advanced and/or metastatic (AJCC Stage IV) disease.

7. Subjects must have received prior hormonal therapy for the treatment of breast cancer as follows:
 - a. Progression must be documented while taking a nonsteroidal aromatase inhibitor including anastrozole or letrozole.
 - b. If hormonal therapy was administered in the adjuvant setting, subjects must have received therapy for at least 6 months prior to developing metastatic disease.
 - c. If hormonal therapy was administered in the metastatic setting, subjects must have received therapy for at least 3 months prior to progression
8. Subjects whose tumors overexpress ErbB2 are eligible provided that they have progressed following therapy which included trastuzumab and/or lapatinib.

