Progression: 25% increase or an increase of 10 sq. cm (whichever is smaller) in the sum of products of measurable lesions over smallest sum observed (over baseline if no decrease), OR appearance of any lesion which had disappeared, OR clear worsening of any evaluable disease, OR appearance of any new lesion/site, OR failure to return for evaluation due to deteriorating condition (unless deterioration is clearly unrelated to this cancer). For scan only bone disease, increased uptake does not constitute clear worsening and new lesions are required for progression. Worsening of existing non-evaluable disease does not constitute progression.

Best Response: This will be calculated from the serial evaluation of objective status. For patients with all disease sites assessed every three to six weeks, two objective determinations of CR, will be required for a best response of CR; two of PR or better, but not qualifying for CR, will be required for PR; two of stable or better, but not qualifying as PR or CR, will be required for stable; and patients with objective status of progression on or before the second evaluation (second AFTER the prestudy evaluation) will have a best response of increasing disease.

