12.0 Statistical Considerations

The response rate with no additional treatment in women with disease progression while receiving aromatase inhibitors is expected to be <5%. We will consider an overall response rate of 20% to be clinically meaningful. For the purpose of this study, response will be defined as clinical benefit rate, including complete response, partial response, and stable disease for at least 12 weeks.

Therefore, we used the American Cancer Society's website (http://cryptnet.net/kepner/one_sample.html) for a 2 stage design with $p_0=0.05$, $p_1=0.20$ and power 80% at $\alpha=5\%$. This design specifies that if 0 of the first 14 eligible and evaluable subjects do not respond to the treatment at 12 weeks, then we are unlikely to reach a true overall response rate of 20%. The 15th patient will not be enrolled until we have confirmed that we have met criteria of at least 1 responses (response defined as clinical benefit) observed in the first 14 patients, to proceed to the second stage. An additional 13 patients will be enrolled in stage 2 for a total of 27 patients. If at least 4 of the total patients respond, we will conclude that the addition of pazopanib in this setting has the possibility of reversing resistance to hormone therapy with aromatase inhibitors. Using this design, we will have a less than 5% chance of incorrectly accepting the null hypothesis ($\alpha=0.05$), and an 80% chance of correctly rejecting the null hypothesis ($\beta=0.2$).

To determine whether the level of cytokines at baseline and during treatment could predict response to antiangiogenic therapy, we will divide patients into two groups; responder and non-responder group. The student t test will be used to analyze the differences of cytokine levels at baseline and at 4 weeks between these 2 groups.

CTC quantification data will be correlated with response and time to progression.

We will make preliminary observations regarding mutations or deletions in PIK3CA and PTEN in patients with measurable CTC, correlating changes with response and disease history, as well as presence or absence of these alterations in archival tumor tissue.

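### Entry progression has no stated criterion and no link to 9.1, so a patient can enter on a change that 9.1 scores as stable and count as clinical benefit without a drug effect

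*Combined protocol and SAP*

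**What the plan says.** **Entry.** Section 3.1 states "Progression must be documented by radiographic studies". Item 7a of 3.2 states "Progression must be documented while taking a nonsteroidal aromatase inhibitor including anastrozole or letrozole". Items 7b and 7c add minimum exposure: 6 months if hormonal therapy was adjuvant, 3 months if it was for metastatic disease. None of these gives a size threshold, a comparison scan or a reference to 9.1. Item 2 of 3.2 accepts evaluable disease, including bone lesions, and cites RECIST 1.1 for measurability.

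**On study.** Section 9.1 uses bidimensional products. Progression is a rise of 25% or 10 sq cm (the smaller) in the summed products over the smallest sum, a new or reappearing lesion, clear worsening of evaluable disease, or failure to return because of deterioration. On bone it says "For scan only bone disease, increased uptake does not constitute clear worsening and new lesions are required for progression". Worsening of existing non-evaluable disease is also not progression. Whatever is not complete response, partial response or progression is stable.

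**Baseline scan.** Item 1a of 3.2 lets routine tests "obtained prior to signed informed consent may be utilized for Screening or Baseline purposes", provided they meet the protocol's specifications. Section 8.0 limits screening and baseline procedures to the 21 days before first dose.

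**Endpoint and rule.** Sections 12.0 and 12.1 count stable disease of at least 12 weeks as benefit. Section 12.0 gives the null as "The response rate with no additional treatment in women with disease progression while receiving aromatase inhibitors is expected to be <5" per cent and the target as "We will consider an overall response rate of 20% to be clinically meaningful". The study continues past stage 1 with at least 1 benefit in 14, and at least 4 of 27 is a positive result.

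**The concern.** Progression appears twice: it must have happened for a patient to enter, and it must not happen by week 12 for the patient to count as benefit. The second use has a definition; the first has none. Where the entry reading is looser than 9.1, the same kind of change qualifies the patient and is later scored as stable.

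The clearest case is bone-only disease. A patient can be called progressing because uptake increased, enter, show a further increase in uptake at week 12, and be scored stable. The same can happen with growth below the 9.1 threshold, or with a worsening effusion in a patient who also has evaluable disease.

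The 5% null is stated for women whose disease is progressing on an aromatase inhibitor. If some entrants have not progressed as the trial defines it, that null does not describe them. The bias runs only toward a positive result, there is no control arm to expose it, and four successes are enough. Section 1.3 says that clinical benefit here could lead to randomized phase II testing.

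**Working it through.** **Inputs from 12.0.** p0 = 0.05, p1 = 0.20, n1 = 14, n2 = 13. Continue if X1 >= 1; success if X1 + X2 >= 4.

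**Step 1: reproduce the design.**

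P(success | p) = sum over x = 1 to 14 of P(X1 = x) × P(X2 >= 4 − x), with X1 ~ Bin(14, p) and X2 ~ Bin(13, p).

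At p = 0.05:

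| x | P(X1 = x) | P(X2 >= 4 − x) | Product |
|---|---|---|---|
| 1 | 0.3593 | 0.0245 | 0.0088 |
| 2 | 0.1229 | 0.1354 | 0.0166 |
| 3 | 0.0259 | 0.4867 | 0.0126 |
| 4 or more | 0.0042 | 1 | 0.0042 |

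The sum is 0.0422. At p = 0.20 the same formula gives 0.8066. The plan's alpha below 5% and power of 80% with 27 patients are reproduced; no design figure is in dispute.

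**Step 2: compare the two uses of progression.**

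| Change seen on the NSAI | Entry (3.1, item 7a) | Week 12 (9.1) |
|---|---|---|
| New lesion | Qualifies | Progression |
| Rise of at least 25% or 10 sq cm in products | Qualifies | Progression |
| Smaller rise | Not excluded | Stable |
| Increased uptake only, scan-only bone disease | Not excluded | Stable |
| Worsening of non-evaluable disease only | Not excluded | Stable |

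The last three rows are the gap. For scale, a 25% rise in a product is a rise of sqrt(1.25) − 1 = 11.8% in each diameter if both grow equally.

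**Step 3: effect on the no-effect rate.** Let f be the share of entrants from the last three rows and s their probability of being stable untreated at week 12. Neither is in the documents. Keep the plan's 5% for everyone else:

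p = (1 − f) × 0.05 + f × s

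With f = 0.10 (assumed; 0.10 × 27 = 2.7 patients):

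- s = 0.3: p = 0.045 + 0.030 = 0.075; P(success) = 0.136
- s = 0.5: p = 0.045 + 0.050 = 0.095; P(success) = 0.244
- s = 0.7: p = 0.045 + 0.070 = 0.115; P(success) = 0.368

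Expected benefits among 27 with no drug effect go from 0.05 × 27 = 1.35 to 0.075 × 27 = 2.03 and 0.115 × 27 = 3.11, against a bar of 4.

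**Step 4: sensitivity to f.** P(success) with no drug effect:

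| f | s = 0.3 | s = 0.5 | s = 0.7 |
|---|---|---|---|
| 5% | 0.08 | 0.12 | 0.17 |
| 10% | 0.14 | 0.24 | 0.37 |
| 20% | 0.27 | 0.52 | 0.73 |

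The false-positive probability reaches 0.10 at a true null rate of 6.7% and 0.20 at 8.7%.

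**The case against.** **The protocol defines progression once, so the word means the same at entry.** This is a fair reading, and some investigators will apply it. But 9.1 is written for on-study evaluation, nothing in 3.1 or 7a points to it, and item 2 cites RECIST 1.1 while 9.1 uses products. The text does not settle which criterion an investigator should apply at entry.

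**Registration is checked.** Section 4.3 has an eligibility checklist and source documents sent to the coordinating center (set out for Yale), and the Study Chair signs off each registration. This is a real safeguard, but the check has no imaging criterion to apply.

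**Most entrants may be unaffected.** Patients who relapse on adjuvant therapy or enter with a new lesion meet 9.1. This stands and limits the share exposed.

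**A reader might go further and infer** that the qualifying scan will routinely be reused as baseline, so that measurement error alone produces many false progressors and a second confirmatory scan is needed. The documents do not support this. Reuse is conditional on the 21-day window and on the scan being obtained as specified. The size of the error effect depends on a measurement error and a pre-entry scan interval that the documents do not give. Such patients would also meet the 25% rule on the reading taken, so that is a different problem from the missing criterion. A mandatory repeat scan could also add a scan and delay entry.

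**Conclusion.** The gap is real, and closing it is a worthwhile, inexpensive improvement. Entry as written does not ensure progression by the definition that scores the endpoint, and the mismatch can only raise the no-effect benefit rate.

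The size is conditional. If 10% of entrants enter on a change that 9.1 calls stable and 30-70% of them are stable untreated at week 12, the chance of a positive conclusion with no drug effect is 0.14-0.37 instead of 0.042. Both inputs are assumptions, and with f near zero the plan's figure stands.

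This does not show that the 5% null is wrong for patients who have truly progressed; the calculation keeps 5% for them. It also does not show that ineligible patients will be enrolled in any particular number.

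**What to change.** 1. Reconcile the bidimensional criteria in 9.1 with the RECIST 1.1 reference in item 2 of 3.2, so that there is one definition to cite.
2. In item 7a, require the qualifying progression to meet the 9.1 definition against an earlier scan on the NSAI, worded so that a first metastatic lesion appearing on adjuvant NSAI qualifies as a new lesion.
3. State in item 7a that increased bone-scan uptake alone does not qualify.
4. Record the basis of the qualifying progression on the CRF: new lesion, size or evaluable disease.
5. Report 12-week benefit by that basis, with a sensitivity analysis limited to patients who met 9.1 at entry.

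Cost: a short eligibility amendment, one CRF field and one added analysis. A few borderline patients become ineligible, and sites must retrieve earlier scans. The sample size of 27 and the 4-of-27 rule do not change, and no extra scan is required.
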